10.1.2.4.4. Additional estimands based on other efficacy endpoints

These estimands of interest are the effect of the randomised treatments on fatigue (MFI), quality of life (SF-36), global assessments of the disease activity reported by the physician (PhGA) and by the patient (PGA), and tear and salivary glands function (Schirmer test, OSS and salivary test), in all patients assuming non-occurrence of IEs. The motivation for this choice is the same as the primary estimand.

The attributes of these estimands are defined as follows:

- Treatment: S95011 or placebo
- Population: RS
- Variable 1: change in SF-36 physical score from baseline to W13
- Variable 2: change in SF-36 mental score from baseline to W13
- Variable 3: change in MFI total score from baseline to W13
- Variable 4: change in PhGA score from baseline to W13
- Variable 5: change in PGA total score from baseline to W13
- Variable 6: change in Schirmer test from baseline to W13
- Variable 7: change in OSS from baseline to W13
- Variable 8: change in stimulated salivary flow score from baseline to W13
- Variable 9: change in unstimulated salivary flow score from baseline to W13
- Summary measure: difference in means between treatments.
- Intercurrent events (IE):
 - change or initiation of unauthorised medication
 - study drug discontinuation for major worsening of primary Sjögren’s syndrome or AE related to study drug
 - study drug discontinuation for other reasons (non-medical reason, AE not-related...)
 - unexpected others events having an major impact on the pharmacologic effect evaluation (they will be defined at the latest in the final version of the SAP).

Main analyses are the same as for the primary estimand. Sensitivity and supplementary analyses are not planned for these estimands.

10.1.2.4.5. Descriptive analyses

For all efficacy endpoints, descriptive statistics will be provided at each visit, by treatment group and also for some efficacy endpoints, by treatment group according to the disease severity and background therapy in RS.

10.1.2.5. Safety analysis

All safety analyses will be performed by treatment group in the Safety Set.

10.1.2.5.1. Adverse events

Number of events, number and percentage of patients reporting at least one event, presented by primary system organ class and/or preferred term (depending on the analysis), will be provided for:

- Serious AE over the analysed period according to the investigator or sponsor opinion,
- Treatment Emergent AE (TEAE), TEAE leading to IMP withdrawal, TEAE requiring new treatment or increase of on-going treatment, TEAE requiring surgical or medical procedure, TEAE related to IMP, serious TEAE, TEAE of Grade 3-4 intensity, non serious TEAE over the corresponding treatment period.

TEAE will be described according to the seriousness, the intensity, the relationship with the IMP, the action taken regarding the IMP, the requirement of added therapy and the outcome.

10.1.2.5.2. Clinical laboratory evaluation

For each laboratory parameter, the following analyses will be performed:

- Descriptive statistics on value at baseline, on value at each post-baseline visit under treatment, on last post-baseline value under treatment and on change from baseline to last post-baseline value under treatment,
- Number and percentage of patients with at least one high/low emergent abnormal value under treatment, according to the laboratory reference ranges and to the cut-offs for PCSA values.
- Laboratory parameters classified (number and percentage of patients in each class) according to these reference ranges and cut-offs, and using shift tables from baseline to the worst (high and/or low) values under treatment.

10.1.2.5.3. Vital signs, clinical examination and other observations related to safety

10.1.2.5.3.1. Vital signs and clinical examination

Vital signs and clinical examination will be described, in terms of value at baseline, value at each post-baseline visit under treatment as well as in terms of change from baseline to each post baseline visit under treatment.

10.1.2.6. Exploratory markers analysis

Cell subsets:

The count of cell subsets will be described using value at each time point and by treatment group.

IL-7, cytokines, and other proteins in blood:

Concentration of circulating proteins will be described using value and by classes (< LLOD, [LLOD ; ULOD], > ULOD) at each time point and by treatment group. Proteins with concentration below LLOQ in more than 70% of all samples will be excluded from analysis

Immune panel, β 2 microglobulin and on the auto-antibody panel:

Concentration of immune panel, β 2 microglobulin and auto-antibody panel will be described using value at each time point and by treatment.

Salivary glands tissue:

Histological analyses and exploratory biomarkers will be described by treatment group.

10.1.2.7. Interim analysis

Only if the recruitment is much longer than expected, a blinded standard deviation reassessment could be planned when 30 patients will have completed the 13-week treatment period as detailed in Section 10.2.

10.2. Determination of sample size

The following efficacy criteria are defined:

- a statistically significant reduction in ESSDAI at Week 13 in the S95011 group compared to placebo, at the one-sided 10% significance level
- an estimated mean reduction in ESSDAI in the S95011 group to be 3 points or greater than placebo. The decrease of 3 points was chosen because it is considered as clinically minimal relevant (Seror *et al*, 2016).

Targeted sample size

With 45 patients in the primary analysis of the primary estimand (30 in the S95011 group and 15 in the placebo group), the study would have around 5% chance of having a false-positive result, *i.e.*, of meeting both the efficacy criteria when the true difference between S95011 and placebo is zero. Additionally, the chances of meeting both the efficacy criteria remain below 14% for true differences between S95011 and placebo of less than 1 point.

The study would have approximately 70% chance of meeting both the efficacy criteria, when the true difference between S95011 and placebo is 4 points. In case the true difference between S95011 and placebo is only 3 points, the study would have approximately 50% chance of meeting both the efficacy criteria. These calculations assume that the primary efficacy endpoint, change from baseline in ESSDAI, follows a normal distribution with a standard deviation of 6. This estimate of the standard deviation is based on some clinical studies (Fisher *et al*, 2020; UCB5857; RO5459072) in patients with primary Sjögren's syndrome in which the observed standard deviation ranged from around 4 to 6.

Blinded standard deviation reassessment

The similar operational characteristics (false-positive and right-positive rates) are obtained with 20 patients in S95011 group and 10 patients in placebo group under assumption of an overall standard deviation of primary efficacy endpoint of 5. So, only if the recruitment is much longer than expected, when 30 patients will have completed the 13-week treatment period, the overall standard deviation of the primary endpoint on non-comparative data could be calculated. If the value is less or equal to 5, the sponsor could stop the patient recruitment, considering that the number of patients is sufficient to meet both efficacy criteria. This potential adaptation has very little or no impact on the probability of having a false-positive result (Kieser, 2003).

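### The 14% limit on a false go for true differences under 1 point is slightly too low: on the plan's own inputs the chance reaches 14.6%

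*Protocol*

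**What the plan says.** Protocol 10.2 defines success by two criteria that must both be met. The first is a significant reduction in ESSDAI against placebo "at the one-sided 10% significance level". The second is "an estimated mean reduction in ESSDAI in the S95011 group to be 3 points or greater than placebo".

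The operating characteristics are given for this design: "With 45 patients in the primary analysis of the primary estimand (30 in the S95011 group and 15 in the placebo group". The change from baseline is assumed to be one that "follows a normal distribution with a standard deviation of 6".

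Four figures follow:

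- No true difference: "the study would have around 5% chance of having a false-positive result".
- A small true difference: "the chances of meeting both the efficacy criteria remain below 14% for true differences between S95011 and placebo of less than 1 point".
- A true difference of 3 points: roughly 50%.
- A true difference of 4 points: "The study would have approximately 70% chance of meeting both the efficacy criteria, when the true difference between S95011 and placebo is 4 points".

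SAP 1.2 repeats the same inputs and the same four figures.

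**The concern.** Three of the four figures are worded as approximate. The 14% figure is not: it is stated as a limit that holds for every true difference under 1 point. A limit of that kind is refuted by one counterexample inside its range, and the plan's own inputs supply one.

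The four figures describe how the proof-of-concept decision rule behaves, and the two low ones tell the reader how often an ineffective or barely effective drug would pass. They should describe the design actually specified. Nothing in the conduct or analysis of the trial hangs on the difference.

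**Working it through.** **Inputs**, all from protocol 10.2: 30 patients on S95011 and 15 on placebo, normal outcome, standard deviation 6, one-sided 10% test, estimated difference of at least 3 points.

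**Standard error.** SE = 6 × √(1/30 + 1/15) = 6 × √0.1 = 1.897.

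**Which criterion governs.** The smallest difference significant at one-sided 10% is 1.2816 × 1.897 = 2.43 points (normal), or 2.47 points (t, 43 df, at standard deviation 6). Both are below 3, so the 3-point rule nearly always decides. To a close approximation,

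P(both criteria met | true difference δ) = 1 − Φ((3 − δ) / 1.897).

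**Reproducing the plan's figures for larger effects.**

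- δ = 4: 1 − Φ(−1/1.897) = 1 − Φ(−0.527) = 70.1%, as stated.
- δ = 3: 1 − Φ(0) = 50.0%, as stated.

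The method and inputs therefore match the plan's.

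**The two low figures by the same formula.**

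- δ = 0: 1 − Φ(3/1.897) = 1 − Φ(1.581) = 5.7%.
- δ approaching 1: 1 − Φ(2/1.897) = 1 − Φ(1.054) = 14.6%.

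**Where 14% is crossed.** Setting the probability to 14% gives (3 − δ)/1.897 = 1.080, so δ = 3 − 1.080 × 1.897 = 0.95.

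**Checks.** The exact joint probability of both criteria, with the standard deviation estimated (t, 43 df), and a simulation of 1,000,000 trials per true difference give:

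| True difference | Plan | Normal formula | Exact joint | Simulation |
|---|---|---|---|---|
| 0 | about 5% | 5.69% | 5.68% | 5.66% |
| 0.90 | under 14% | 13.42% | 13.39% | – |
| 0.95 | under 14% | 14.00% | 13.97% | – |
| 0.99 | under 14% | 14.47% | 14.44% | – |
| 1.00 (limit) | – | 14.59% | 14.56% | 14.58% |
| 3 | about 50% | 50.0% | 49.95% | 49.90% |
| 4 | about 70% | 70.09% | 70.05% | 70.00% |

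Using 39 df, as for the planned model with baseline, treatment and a four-class stratification factor (45 − 6 parameters), gives 5.67% at zero and 14.55% at 1 point. The result does not depend on the choice of z or t.

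**Could another input explain the stated figures?** Some come close at the low end: 32 and 16 patients give 5.1% and 13.8%; a standard deviation of 5.77 gives 5.0% and 13.7%; a one-sided 5% test (normal) gives 5.0% and 13.2%, but then 47.5% and 67.8% at 3 and 4 points. Neither document states any of these.

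**The case against.** The strongest defence is that all four figures reproduce to within 0.7 percentage points, and that the input behind them is uncertain by far more. Both documents report standard deviations of around 4 to 6 in earlier studies, and the plan takes the top of that range. With 30 and 15 patients the chance at no difference is 0.9%, 2.9% and 5.7% for standard deviations of 4, 5 and 6; at 1 point it is 5.7%, 10.3% and 14.6%. So 5.7% and 14.6% are the least favourable values within the cited range. This stands, and it is why the point is minor. It does not rescue the limit, which is stated for a standard deviation of 6.

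A second defence is that the primary model adjusts for baseline, which can reduce the residual standard deviation. If the correlation between baseline and change were about 0.27 (an assumption), the residual value would be 6 × √(1 − 0.27²) = 5.78, and all four stated figures would fit. But the sample-size sections attach their figures to a standard deviation of 6 and mention no such gain.

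A reader might also infer more than the documents support:

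- *That the no-effect figure is an error, with the true rate about one seventh higher.* It is worded as approximate, and 5.7% is a loose fit to it, not a contradiction. A ratio taken against a rounded number is false precision.
- *That the two low figures were truncated instead of rounded.* Neither document says how they were obtained.
- *That the smaller option of 20 and 10 patients with a standard deviation of 5 is misdescribed.* It gives 6.0% at zero and 14.9% at 1 point, which is similar to the main design, and similarity is all that is claimed. SAP 5 records that the reassessment was not carried out.
- *That type I error control is affected.* The test level is set separately at one-sided 10%, and 5.7% lies well inside it.

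**Conclusion.** Wrong as written, at the lowest severity. The 14% limit does not hold for true differences between about 0.95 and 1 point, where the chance rises to just under 14.6%. The excess is at most 0.6 percentage points; up to about 0.95 points the limit is correct.

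This rests on the plan's own assumptions: 45 patients contributing in full, normality and a standard deviation of 6. If 10% of the information were lost (27 and 13.5 patients), the normal formula gives 6.7% at zero and 15.9% at 1 point, but the plan states its figures for 45 in the primary analysis and imputes after intercurrent events.

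**What to change.** In protocol 10.2 and SAP 1.2, raise the limit for true differences under 1 point from 14% to 15%. As an optional tidy-up in the same sentences, give the chance at zero difference as around 6%. Leave the 50% and 70% figures as they are.

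The cost is two numbers in two documents, each slightly less favourable than now. Sample size, success criteria and analyses are untouched.

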10.3. Pharmacokinetic analysis and PK/PD analysis

Serum concentrations of S95011 will be analysed by a population modelling approach, described in a separated Data Analysis Plan (DAP), in order to assess the pharmacokinetics of the drug and to investigate potential sources of variability through a covariate analysis. This analysis will provide pharmacokinetic parameters and their associated variability in patients and will be the object of a separate report.

Exploratory assessment of the relationship between exposure and pharmacodynamics (as safety and efficacy) will be performed and if applicable, population pharmacokinetic-pharmacodynamic (PK/PD) models will be developed and a DAP will be set up and reported separately.

11. DIRECT ACCESS TO SOURCE DATA / DOCUMENTS

The investigator will allow the monitors, the persons responsible for the audit, the representatives of the IRB/IEC, and of the Competent Authorities to have direct access to source data / documents.

12. QUALITY CONTROL AND QUALITY ASSURANCE

12.1. Study monitoring

Clinical site monitoring is conducted to ensure that the rights and well-being of human patients are protected, that the reported trial data are accurate, complete, and verifiable, and that the conduct of the trial is in compliance with the currently approved protocol/amendment(s), with GCP, and with applicable regulatory requirement(s).

Monitoring for this study will be performed by the structure mentioned in [Section 1](#).

Details of clinical site monitoring are documented in a Clinical Monitoring Plan (CMP). The CMP describes in detail who will conduct the monitoring, at what frequency monitoring will be done, at what level of detail monitoring will be performed, and the distribution of monitoring reports.

Independent audits may be conducted to ensure monitoring practices are performed consistently across all participating sites and that monitors are following the CMP.

12.1.1. Before the study

The investigator will allow the monitor to visit the site and facilities where the study will take place in order to ensure compliance with the protocol requirements.

Training sessions may be organised for the investigators and/or instruction manuals may be given to the investigators.

12.1.2. During the study

The investigator will allow the monitor to:

- Review the study site's processes and procedures,
- Verify appropriate clinical investigator supervision of study site staff and third party vendors,
- Inspect the site, the facilities and the material used for the study,
- Meet all members of his/her team involved in the study,
- Consult the documents relevant to the study,
- Have access to the electronic case report forms,
- Check that the electronic case report forms have been filled out correctly,
- Directly access source documents for comparison of data therein with the data in the electronic case report forms,
- Verify that the study is carried out in compliance with the protocol and local regulatory requirements.

The study monitoring will be carried out at regular intervals, depending on the recruitment rate and / or the investigation schedule, and arranged between the investigator and monitor.

All information dealt with during these visits will be treated as strictly confidential.

12.2. Computerised medical file

If computerised medical files are used, and if the computer system allows, no change made in the medical files by the investigator should obscure the original information. The record must clearly indicate that a change was made and clearly provide a means to locate and read the prior information (*i.e.* audit trail). The investigator will save data at regular intervals.

The investigator must guarantee the integrity of the study data in the medical files by implementing security measures to prevent unauthorised access to the data and to the computer system.

If the computerised medical files are considered as not validated by the sponsor, the investigator undertakes:

- at the start of the study, to print the medical files of all patients allowing a reliable verification of the study criteria (*e.g.* medical history/previous treatments/ characteristics of the studied disease documented within the period of time defined by the study protocol),
- during the study, to print in real time each data entry and each data change.

The investigator will personally sign, date and give the number of pages on the first or last page of each print-out. At each visit by the monitor, the investigator will provide all the print-outs of the medical files of the patients. The monitor will personally sign and date the first (or last) page then initial all pages in each paper print-out.

If the computer system allows the tracking of the changes made to the medical files, the investigator will supply the monitor, at each visit, with a print-out of the medical files of the patients and the records of the changes made. Each print-out will be personally dated and signed, by the investigator and the monitor on the first page. The number of pages will also be indicated by the investigator and the monitor on the first page.

If the computerised medical files are considered as validated by the sponsor, the investigator undertakes to give access to the monitor to the computerised medical files of all patients. If the monitor cannot access to the tracking of the changes made to the medical files, the investigator will supply the monitor, at each visit, with a print-out of the records of the changes made to the medical files of the patients. Each print-out will be personally dated and signed, by the investigator and the monitor on the first page. The number of pages will also be indicated by the investigator and the monitor on the first page.

The investigator undertakes to keep:

- All medical file print-outs signed and dated by him/her and by the monitor when the computer system is considered as not validated by the sponsor,
- If the computer system used allows changes to be made, the print-outs of the audit trail when the computer system is considered as not validated by the sponsor or when the monitor cannot access to the audit trail in the computer system,
- All original source-documents (originals of specific examinations, informed consent forms, therapeutic unit tracking form...).

12.3. Audit - Inspection

The investigator should be informed that an audit may be carried out during or after the end of the study.

The investigator should be informed that the Competent Authorities may also carry out an inspection in the facilities of the sponsor and/or the study centre(s). The sponsor will inform the investigators concerned immediately upon notification of a pending study centres inspection. Likewise, the investigator will inform the sponsor of any pending inspection.

The investigator must allow the representatives of the Competent Authorities and persons responsible for the audit:

- to inspect the site, facilities and material used for the study,
- to meet all members of his/her team involved in the study,
- to have direct access to study data and source documents,
- to consult all of the documents relevant to the study.

If the computerised medical file is considered as not validated, the investigator undertakes to provide all the source-documents and the print-outs of the medical files of the patients and, if the computer system used allows, the record of the changes made during the study.

If the computerised medical file is considered as validated, the investigator undertakes to:

- give access to the representatives of the Competent Authorities and persons responsible for the audit to the computerised medical files of all patients,
- provide the print-outs of the changes made during the study, if the tracking of the changes made to the medical files cannot be accessed in the computer.

12.4. Supervisory committees

DSMB recommendations will be forwarded to the IRB/IEC/ Regulatory Agencies only if relevant for the safety of patients.

All along the study, in order to ensure patients' safety, the DSMB will review patients' safety data, including ERIN and adverse events leading to individual premature IMP discontinuation. In addition, unscheduled urgent DSMB meetings will be triggered if required (see [Sections 4.4.1](#) and [8.10](#)).

The DSMB will treat all data as strictly confidential and will not disclose them to anyone else than members of the DSMB.

The role and organization of the DSMB are detailed in a separate DSMB charter, specifying the safety criteria for which the study should be discontinued.

13. ETHICS

13.1. Institutional Review Board(s)/Independent Ethics Committee(s)

The study protocol, the "Participant information and consent form" document, the list of investigators document, the insurance documents, the Investigator's Brochure of administered IMP will be submitted to (an) IRB(s)/IEC(s) by the investigator(s) or the national coordinator(s) or the sponsor in accordance with local regulations.

The study will not start in a centre before written approval by corresponding IRB/IEC(s) has been obtained, the local regulatory requirements have been complied with, and the signature of the clinical study protocol of each contractual party involved has been obtained.

13.2. Study conduct

The study will be performed in accordance with the ethical principles stated in the Declaration of Helsinki 1964, as revised in Fortaleza, 2013 (see [Appendix 1](#)) with the GCP and with the applicable regulatory requirements.

